# 3.2 Responsibility for Analyses/In-house Blinding

The statistical analysis of the data obtained from this study will be the responsibility of the Clinical Biostatistics department of the Sponsor.

This study will be conducted as a double-blind study under in-house blinding procedures. The official, final database will not be unblinded until medical/scientific review has been performed, protocol deviations have been identified, and data have been declared final and complete.

The Clinical Biostatistics department will generate the randomized allocation schedule(s) for study intervention assignment. Randomization will be implemented using an IRT.

Blinding issues related to the planned interim analyses are described in Section 3.7.

## 3.3 Hypotheses/Estimation

Supplemental SAP

Objectives of the study are stated in Section 3 of the protocol. This is an estimation study, and no formal hypothesis testing will be performed.

# 3.4 Analysis Endpoints

## 3.4.1 Immunogenicity Endpoints

Immune responses will be measured for each of the following serotypes contained in V114: 1, 3, 4, 5, 6A, 6B, 7F, 9V, 14, 18C, 19A, 19F, 22F, 23F, and 33F.

The primary immunogenicity analysis endpoint is:

• Anti-PnPs serotype-specific IgG GMCs at 30 days postvaccination (Day 30) with V114 or Prevnar 13TM.

The secondary immunogenicity analysis endpoints include:

- Anti-PnPs serotype-specific OPA GMTs at 30 days postvaccination (Day 30) with V114 or Prevnar 13TM.
- Anti-PnPs serotype-specific OPA GMTs and IgG GMCs at 30 days postvaccination with PNEUMOVAXTM23 (Week 12).

The exploratory immunogenicity analysis endpoint includes:

• Anti-PnPs serotype-specific GMFRs from prevaccination (Day 1) to 30 days postvaccination (Day 30) with V114 or Prevnar 13TM for both OPA and IgG responses.

## 3.4.2 Safety Endpoints

A description of safety measures is presented in Sections 8.3 and 8.4 of the protocol. The method of safety analysis is described in Section 3.6.2.

Safety and tolerability will be assessed by clinical review of all relevant parameters including adverse events and postvaccination temperature measurements following V114 or Prevnar 13TM and PNEUMOVAXTM23 (separately).

The safety analysis endpoints include:

- Proportion of participants with solicited injection-site AEs (redness/erythema, swelling, tenderness/pain, and hard lump/induration) from Day 1 through Day 14 postvaccination
- Proportion of participants with solicited systemic AEs (muscle pain/myalgia, joint pain/arthralgia, headache, tiredness/fatigue, and hives or welts/urticaria) from Day 1 through Day 14 postvaccination
- Proportion of participants with the broad AE categories consisting of any AE and a vaccine-related AE from Day 1 through Day 14 postvaccination
- Proportion of participants with an SAE, a vaccine-related SAE, a discontinuation due to an AE, and a death from Day 1 through Month 6 (ie, 6 months postvaccination with V114 or Prevnar 13TM)
- Proportion of participants with maximum temperature measurements meeting the Brighton Collaboration cut points from Day 1 through Day 7 postvaccination

The timeframe associated with the reporting of AEs is consistent with the collection. Nonserious adverse events (NSAEs) are reported from Day 1 through Day 14 following each vaccination. SAEs are reported from Day 1 (following vaccination with PCV [V114 or Prevnar 13TM]) through Week 8 (prior to vaccination with PPV23 [PNEUMOVAXTM23]) and from Week 8 (following vaccination with PPV23) through Month 6 (completion of study participation).

#### 3.5 **Analysis Populations**

#### 3.5.1 **Immunogenicity Analysis Populations**

The Per-Protocol (PP) population will serve as the primary population for the analysis of immunogenicity data in this study. The PP population consists of all randomized participants without deviations from the protocol that may substantially affect the results of the immunogenicity endpoint. Potential deviations that may result in the exclusion of a participant from the PP population for all immunogenicity analyses include:

- Failure to receive study vaccine at Visit 2 (Day 1)
- Failure to receive correct clinical material as per randomization schedule (ie, a participant who was randomized to V114 but received Prevnar 13TM, or vice versa)
- Receipt of a prohibited medication or prohibited vaccine prior to study vaccination

Additional potential deviations that may result in the exclusion from the PP population for specific immunogenicity analyses (depending on the time point) include:

- Failure to receive PNEUMOVAXTM23 at Visit 4 (Week 8)
- Receipt of a prohibited medication or prohibited vaccine prior to a blood sample collection
- Collection of a blood sample outside of the pre-specified window (as described in Section 1.3 of the protocol)

The final determination on protocol deviations, and thereby the composition of the PP population, will be made prior to the final unblinding of the database.

A supportive analysis using the Full Analysis Set (FAS) population will also be performed for the primary immunogenicity endpoint. The FAS population consists of all randomized participants who received the relevant study vaccination(s) and have at least 1 serology result relevant to the timepoint of interest (ie, a participant who was randomized and missed the vaccination at Visit 2 [Day 1] is removed from the FAS population at all visits; a participant who was randomized and missed vaccination at Visit 4 [Week 8] is removed from the FAS population at Visit 5 [Week 12]). Participants will be included in the vaccination group to which they are randomized for the analysis of immunogenicity data using the FAS population.

#### 3.5.2 **Safety Analysis Populations**

Safety analyses will be conducted on the APaT population, which consists of all randomized participants who received the relevant study vaccination for the timepoint of interest (ie, a participant must receive a single dose of V114 or Prevnar 13TM at Visit 2 [Day 1] to be included in the analyses following PCV; a participant must receive a single dose of PNEUMOVAXTM23 at Visit 4 [Week 8] to be included in the analyses following PPV23). Participants will be included in the group corresponding to the study vaccination they actually received for the analysis of safety data using the APaT population. This will be the group to which they are randomized except for participants who take incorrect study vaccination; such participants will be included in the treatment group corresponding to the study vaccination actually received.

At least 1 temperature measurement obtained after study intervention is required for inclusion in the analyses of temperature.

#### 3.6 **Statistical Methods**

Statistical methods for immunogenicity and safety analyses are described in Section 3.6.1 and Section 3.6.2, respectively. Section 3.6.3 describes how demographic and baseline characteristics will be summarized.

The correct stratum will be used for analysis regardless of the assigned stratum at randomization (ie, stratification errors will be corrected for the purposes of analysis).

#### **Statistical Methods for Immunogenicity Analyses** 3.6.1

This section describes the statistical methods that address the primary, secondary, and exploratory immunogenicity objectives.

Immunogenicity analyses will be conducted for each of the 15 pneumococcal serotypes contained in V114 separately. To address the primary immunogenicity objective, evaluation of the serotype-specific IgG GMCs at 30 days post-vaccination with V114 or Prevnar 13TM (Day 30) will include descriptive summaries and within-group 95% CIs to be calculated for each vaccination group. Point estimates for the IgG GMCs will be calculated by exponentiating the estimates of the mean of the natural log values. The within-group CIs will be derived by exponentiating the CIs of the mean of the natural log values based on the tdistribution.

A similar statistical approach will be used to evaluate serotype-specific OPA responses at Day 30, and IgG and OPA responses at 30 days postvaccination with PNEUMOVAXTM23 (Week 12) for each vaccination group. To address the exploratory immunogenicity objective, point estimates and within-group 95% CIs will be provided for serotype-specific GMFRs from Day 1 to Day 30 for both IgG and OPA responses. The point estimates will be calculated by exponentiating the estimates of the mean of the natural log values, and the within-group CIs will be derived by exponentiating the bounds of the CIs of the mean of the natural log values based on the t-distribution.

Reverse Cumulative Distribution Curves for OPA titers and IgG concentrations will be graphically displayed by serotype at each of the following timepoints: Day 30 and Week 12.

A detailed analysis strategy for key immunogenicity endpoints is listed in **Table 1**.

Table 1 Analysis Strategy for Immunogenicity Variables

Endpoint/Variable (Description, Time Point)	Primary vs. Supportive Approach †	Statistical Method	Analysis Population	Missing Data Approach	
Primary Endpoint					
A L' D. D. L. C. CMC. A. D. 20	P	Descriptive Statistics	PP	Missing data will not be imputed	
Anti-PnPs IgG GMCs at Day 30	S	(estimate, 95% CI)	FAS		
Secondary Endpoints					
Anti-PnPs OPA GMTs at Day 30	P	Descriptive Statistics (estimate, 95% CI)	PP	Missing data will not be imputed	
Anti-PnPs IgG GMCs/OPA GMTs at Week 12	P	Descriptive Statistics (estimate, 95% CI)	PP	Missing data will not be imputed	

 $^{\dagger}$  P = primary approach; S = supportive approach.

The detectable ranges for OPA and IgG responses differ across serotypes. The limits of quantitation define the range of responses over which the assays provide precise and accurate measurements. **Table 2** gives the limits of quantitation defined for each serotype for OPA and IgG responses. For responses smaller than the lower limit of quantitation (LLOQ), half of the LLOQ is used for analysis when calculating the OPA GMTs and IgG GMCs, and in the graphical displays of the Reverse Cumulative Distribution Curves for OPA titers and IgG concentrations. The value of the LLOQ is used for analysis when calculating the GMFR for OPA and IgG responses. For OPA and IgG responses that are larger than the upper limit of quantitation (ULOQ), a value equal to the ULOQ + 1 is used for analysis.

CI = confidence interval; FAS = Full Analysis Set; GMC = Geometric Mean Concentration; GMFR = Geometric Mean Fold Rise; GMT = Geometric Mean Titer; IgG = immunoglobulin G;

OPA = opsonophagocytic activity; PnPs = pneumococcal polysaccharide; PP = Per-Protocol.

Limits of Quantitation for OPA and IgG Serotype-specific Responses Table 2

	OPA		IgG	
Serotype	LLOQ (1/dil)	ULOQ (1/dil)	LLOQ (μg/mL)	ULOQ (μg/mL)
1	9	30,213	0.05	850
3	19	30,564	0.05	145
4	34	137,160	0.05	173
5	27	119,016	0.10	368
6A	232	210,600	0.05	393
6B	40	105,840	0.05	341
7F	61	251,235	0.05	830
9V	151	224,316	0.05	644
14	62	281,637	0.05	1,520
18C	115	445,230	0.05	730
19A	31	128,304	0.05	1,387
19F	113	158,841	0.05	1,461
22F	15	229,338	0.05	1,054
23F	55	251,829	0.05	595
33F	20	399,600	0.05	833

IgG = immunoglobulin G; LLOQ = lower limit of quantitation; OPA= opsonophagocytic activity; ULOQ = upper limit of quantitation.

#### 3.6.2 **Statistical Methods for Safety Analyses**

Safety and tolerability will be assessed by clinical review of all relevant parameters including AEs and postvaccination temperature measurements.

The analysis strategy for safety parameters following each vaccination is summarized in **Table 3.** The proportion of participants with solicited injection-site AEs (redness/erythema, swelling, tenderness/pain, and hard lump/induration from Day 1 to Day 14 postvaccination) and solicited systemic AEs (muscle pain/myalgia, joint pain/arthralgia, headache, tiredness/fatigue, and hives or welts/urticaria from Day 1 to Day 14 postvaccination) will be provided along with the corresponding within-group 95% CIs (based on the exact binomial method proposed by Clopper and Pearson [Clopper, C. J. 1934]). In addition, the broad AE categories consisting of the proportion of participants with any AE, a vaccine-related AE, a SAE, an AE which is both vaccine-related and serious, discontinuation due to an AE, and death will be summarized in the same manner. The proportion of participants with maximum temperature measurements meeting the Brighton Collaboration cut points (from Day 1 through Day 7) will also be provided along with the corresponding within-group 95% CIs. Point estimates by vaccination group will be provided for all other safety parameters (specific AE terms and system organ class terms).

The analysis of safety parameters will be evaluated at 2 separate time points: (1) following administration of V114 or Prevnar 13TM and (2) following administration of PNEUMOVAXTM23. Descriptive summaries of AEs following administration of V114 or Prevnar 13TM will include nonserious AEs within 14 days of vaccination and SAEs occurring Day 1 through Week 8 (prior to vaccination with PPV23). Descriptive summaries of AEs following administration of PNEUMOVAXTM23 will include nonserious AEs within 14 days of vaccination and SAEs occurring Week 8 (following vaccination with PPV23) through Month 6 (completion of study participation).

Table 3 Analysis Strategy for Safety Parameters Following Each Vaccination

Safety Endpoint	Within-Group 95% CI	Descriptive Statistics
Injection-site redness/erythema (Days 1 to 14) †	X	X
Injection-site swelling (Days 1 to 14)†	X	X
Injection-site tenderness/pain (Days 1 to 14) $^{\dagger}$	X	X
Injection-site hard lump/induration (Days 1 to $14$ ) †	X	X
Muscle pain/myalgia (Days 1 to 14) †	X	X
Joint pain/arthralgia (Days 1 to 14) †	X	X
Headache (Days 1 to 14) †	X	X
Tiredness/fatigue (Days 1 to 14) †	X	X
Hives or welts/urticaria (Days 1 to 14)†	X	X
Any AE ‡	X	X
Any vaccine-related AE ‡	X	X
Any SAE ‡	X	X
Any vaccine-related SAE ‡	X	X
Discontinuation due to AE ‡	X	X
Death ‡	X	X
Maximum temperature measurements meeting the Brighton Collaboration cut points (Days 1 to 7)	X	X
Specific AEs by SOCs and PT		X

† Includes solicited events only.

Safety analyses will be based on the observed data (ie, with no imputation of missing data).

<sup>‡ These endpoints are broad adverse event categories. For example, descriptive statistics for the safety endpoint of "Any AE" will provide the number and percentage of participants with at least 1 AE.

AE = adverse event; CI = confidence interval; PT = preferred term; SAE = serious adverse event; SOC = system organ class; X = results will be provided.

Laboratory AEs will not be reported in summary tables as laboratory safety testing is not performed as part of the study and, therefore, any such AEs would only be reported spontaneously. A listing of laboratory AEs will be provided.

A supportive analysis summarizing the proportion of participants reporting each of the solicited complaints on the VRC will be conducted in support of the primary safety analyses that are based on solicited AEs. This supportive analysis will use the methodology specified in **Table 3** for solicited AEs. The analysis will be conducted on the subset of the APaT population who entered solicited complaints data on the VRC.

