## 3 HYPOTHESES, OBJECTIVES, AND ENDPOINTS

There is no formal hypothesis testing in this study.

Objectives	Endpoints					
Primary						
Objective: To evaluate the safety and tolerability of V114 with respect to the proportion of participants with adverse events (AEs).	
 
Following vaccination with V114:
 
Solicited injection-site AEs from Day 1 through Day 14 postvaccination
 
Solicited systemic AEs from Day 1 through Day 14 postvaccination
 
Vaccine-related serious adverse events (SAEs) through completion of study participation
 
					
• Objective: To evaluate the anti-pneumococcal polysaccharide (PnPs) serotype-specific Immunoglobulin G (IgG) Geometric Mean Concentrations (GMCs) at 30 days postvaccination (Day 30) with V114 or Prevnar 13 TM by each vaccination group.	Anti-PnPs serotype-specific IgG responses for the 15 serotypes contained in V114 at Day 30					

27-MAR-2019

V114-030-00 FINAL PROTOCOL

	Objectives	Endpoints					
Sec	condary						
•	Objective: To evaluate the safety and tolerability of PNEUMOVAX TM 23 administered 8 weeks following V114 with respect to the proportion of participants with AEs.	Following vaccination with PNEUMOVAX TM 23:  • Solicited injection-site AEs from Day 1 through Day 14 postvaccination  • Solicited systemic AEs from Day 1 through Day 14 postvaccination					
•	Objective: To evaluate the anti-PnPs serotype-specific opsonophagocytic activity (OPA) Geometric Mean Titers (GMTs) at 30 days postvaccination (Day 30) with V114 or Prevnar 13 TM by each vaccination group.	Anti-PnPs serotype-specific OPA responses for the 15 serotypes contained in V114 at Day 30					
•	Objective: To evaluate the anti-PnPs serotype-specific OPA GMTs and IgG GMCs at 30 days postvaccination with PNEUMOVAX TM 23 (Week 12) by each vaccination group.	Anti-PnPs Serotype-specific OPA and IgG responses for the 15 serotypes contained in V114 at Week 12					
Te	rtiary/Exploratory						
•	Objective: To evaluate the Anti-PnPs serotype-specific Geometric Mean Fold Rises (GMFRs) from prevaccination (Day 1) to 30 days postvaccination (Day 30) with V114 or Prevnar 13 TM for both OPA and IgG responses by each vaccination group.	Anti-PnPs serotype-specific OPA and IgG responses for the 15 serotypes contained in V114 at Day 1 and Day 30					

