#### 9.6.2 **Statistical Methods for Safety Analyses**

Safety and tolerability will be assessed by clinical review of all relevant parameters including AEs and postvaccination temperature measurements.

The analysis strategy for safety parameters following each vaccination is summarized in Table 5. The proportion of participants with solicited injection-site AEs (redness/erythema, swelling, tenderness/pain, and hard lump/induration Day 1 to Day 14 postvaccination) and solicited systemic AEs (muscle pain/myalgia, joint pain/arthralgia, headache, tiredness/fatigue, and hives or welts/urticaria from Day 1 to Day 14 postvaccination) will be provided along with the corresponding within-group 95% CIs (based on the exact binomial method proposed by Clopper and Pearson [Collett, D. 1999]. In addition, the broad AE categories consisting of the proportion of participants with any AE, a vaccine-related AE, a SAE, an AE which is both vaccine-related and serious, discontinuation due to an AE, and death will be summarized in the same manner. The proportion of participants with maximum temperature measurements meeting the Brighton Collaboration cut points (from Day 1 through Day 7) will also will be provided along with the corresponding within-group 95% CIs. Point estimates by vaccination group will be provided for all other safety parameters (specific AE terms and system organ class terms).

The analysis of safety parameters will be evaluated at 2 separate time points: (1) following administration of V114 or Prevnar 13TM and (2) following administration of PNEUMOVAXTM23. Descriptive summaries of AEs following administration of V114 or Prevnar 13TM will include nonserious AEs within 14 days of vaccination and SAEs occurring

Confidential

27-MAR-2019

CI = confidence interval; FAS = Full Analysis Set; GMC = Geometric Mean Concentration; GMFR = Geometric Mean Fold Rise; GMT = Geometric Mean Titer; IgG = immunoglobulin G; OPA = opsonophagocytic activity; PnPs = pneumococcal polysaccharide; PP = Per-Protocol

Day 1 through completion of study participation. Descriptive summaries of AEs following administration of PNEUMOVAXTM23 will include nonserious AEs within 14 days of vaccination and SAEs through completion of study participation.

Table 5 Analysis Strategy for Safety Parameters Following Each Vaccination

Safety Endpoint	Within-Group 95% CI	Descriptive Statistics

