# 3 ANALYTICAL AND METHODOLOGICAL DETAILS

# 3.1 Statistical Analysis Plan Summary

Key elements of the statistical analysis plan are summarized below; the comprehensive plan is provided in Sections 3.2 through 3.12.

Study Design Overview  Intervention Assignment	A Phase 3, Multicenter, Randomized, Double-blind, Active Comparator-controlled Study to Evaluate the Safety, Tolerability, and Immunogenicity of V114 Followed by Administration of PNEUMOVAX TM 23 Eight Weeks Later in Children Infected with Human Immunodeficiency Virus (HIV) (PNEU–WAY PED)  Participants will be randomly assigned in a 1:1 ratio to V114 or		
	Prevnar 13 ™ , respectively.		
Analysis Populations	Immunogenicity: Per-Protocol (PP) Safety: All Participants as Treated (APaT)		
Primary Endpoint(s)	
 
Immunogenicity:         
 
Anti-PnPs serotype-specific IgG GMCs for the 15 serotypes contained in V114 at 30 days postvaccination with V114 or Prevnar 13TM
 
 
 
Safety:         
 
Proportion of participants with solicited injection-site AEs (redness/erythema, swelling, tenderness/pain, and hard lump/induration) from Day 1 through Day 14 following V114 or Prevnar 13TM
 
Proportion of participants with solicited systemic AEs (muscle pain/myalgia, joint pain/arthralgia, headache, tiredness/fatigue, and hives or welts/urticaria) from Day 1 through Day 14 following V114 or Prevnar 13TM
 
Proportion of participants with vaccine-related SAEs through completion of study participation
 
 
 
		
Key Secondary Endpoints	
 
Immunogenicity:
 
Anti-PnPs serotype-specific OPA GMTs for the 15 serotypes contained in V114 at 30 days postvaccination with V114 or Prevnar 13TM
 
Anti-PnPs serotype-specific OPA GMTs and IgG GMCs at 30 days postvaccination with PNEUMOVAXTM23 (Week 12)
 
		

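### The sSAP defines vaccine-related SAEs to the end of participation but stops the post-PCV SAE summary at Week 8, so no specified table gives the Day 1 to Month 6 proportion

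*Combined protocol and SAP*

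**What the plan says.** Four places run the endpoint over the whole of follow-up.

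- Protocol Section 3 lists, among three primary safety endpoints under V114, "Vaccine-related serious adverse events (SAEs) through completion of study participation".
- sSAP 3.1 keeps it as a primary endpoint: "Proportion of participants with vaccine-related SAEs through completion of study participation".
- The endpoint list in sSAP 3.4.2 has "Proportion of participants with an SAE, a vaccine-related SAE, a discontinuation due to an AE, and a death from Day 1 through Month 6", and explains Month 6 as six months after the PCV dose.
- Protocol 9.6.2 summarises SAEs after PCV from "Day 1 through completion of study participation".

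Two places in the sSAP cut it short. The closing paragraph of 3.4.2 splits SAE reporting at Week 8. Section 3.6.2 then states that the summary after PCV will contain "nonserious AEs within 14 days of vaccination and SAEs occurring Day 1 through Week 8 (prior to vaccination with PPV23", and the summary after PPV23 will contain "SAEs occurring Week 8 (following vaccination with PPV23) through Month 6 (completion of study participation". It describes safety as evaluated at two time points, one per vaccination, and names no third summary.

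sSAP 3.5.2 restricts the second summary: a child must have had PNEUMOVAX 23 "at Visit 4 [Week 8] to be included in the analyses following PPV23". Protocol 7.1 and 8.12.3 keep children who stop vaccination early in safety follow-up.

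**The concern.** A statistician who programs sSAP 3.6.2 as written will not produce the primary endpoint that sSAP 3.1 defines. The post-PCV table stops about eight weeks after V114, while the endpoint and the design follow the child for about six months from that dose. The rest of the V114 follow-up is reported under a different vaccine and in a different population.

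What is at stake is the headline V114 safety proportion and its confidence interval. A reader of the report could take an eight-week percentage for the six-month one. The reason would be hard to trace. The sSAP change log mentions the added paragraph in 3.4.2 as a clarification, and its entries for 3.6.2 do not mention the SAE window.

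**Working it through.** **Inputs.** From the Schedule of Activities (protocol 1.3), counted from Visit 2: Visit 4 falls on Day 56 to 70, and the final telephone contact on Day 166 to 194, midpoint (166 + 194)/2 = 180. Group size is 200 (sSAP 3.9.2). The number of children who will miss PPV23 is not given.

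**The plan's own figures.** The plan gives none for the share of follow-up covered. Its only SAE calculations are in sSAP 3.9.2, and they reproduce:

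- 1 − (1 − 0.008)^200 = 79.9% (stated 80%)
- 1 − (1 − 0.0035)^200 = 50.4% (stated 50%)
- zero-event bound 1 − 0.025^(1/200) = 1.83% (stated 1.82%)

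They concern any SAE and carry no time window, so nothing below rests on them.

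**Step 1: which table would carry the endpoint?** sSAP Table 3 has rows for any SAE, vaccine-related SAE and death, but attaches no window to them and is laid out per vaccination. The windows come from 3.6.2, and neither runs from Day 1 to Month 6. A death is an SAE by definition (protocol Appendix 3), so it follows the same split.

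**Step 2: share of follow-up time in the post-PCV summary.** Share = day of Visit 4 / day of final contact.

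- Smallest: 56/194 = 28.9%
- Nominal: 56/180 = 31.1%
- Largest: 70/166 = 42.2%

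Between 57.8% and 71.1% of follow-up time therefore lies outside it.

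**Step 3: can the two summaries be added?** Let N1 be the children given a PCV and N2 those who also received PPV23, with N2 no larger than N1. Let A be the children with an SAE in the first window, B the PPV23 recipients with one in the second, AB those in both, and C the children without PPV23 whose first SAE comes after Week 8. Then

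proportion with an SAE, Day 1 to Month 6 = (A + B − AB + C)/N1.

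The two summaries give A/N1 and B/N2. AB is not reported and C is not tabulated, so the endpoint cannot be recovered from them.

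**Step 4: the children counted in C.** After Week 8 each child without PPV23 has 166 − 70 = 96 to 194 − 56 = 138 days in neither summary. If 2% to 10% miss PPV23 (an assumption), that is 4 to 20 children per group of 200. The share of the group's follow-up time affected is then 0.02 × 0.578 = 1.2% to 0.10 × 0.711 = 7.1%. These are children and time at risk, not events.

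**The case against.** The case for leaving the plan alone has real substance.

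- *The long window is still in the sSAP.* Section 3.1 and the list in 3.4.2 keep it, and Section 1 describes the sSAP's changes as not principal in nature, so the team may well produce the Month 6 proportion. This stands to the extent that the plan is contradictory and not settled on the wrong answer. It does not supply the missing table.
- *The split has a purpose.* Under protocol 9.6.2 both SAE windows ran to the end, so an SAE after PPV23 counted under both vaccines. Separate windows help attribution. This stands, and is a reason to keep them as additional tables.
- *Little may change.* Causality under Appendix 3 depends on a plausible time course, so related SAEs may come mostly in the first weeks. This stands.
- *The study is descriptive.* No hypothesis or success criterion depends on the figure, SAEs are collected throughout, and the DMC reviews safety data. This limits the harm, but a primary endpoint still needs an analysis that matches its definition.

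A reader might go further and infer that most SAEs after V114 disappear from the results. The documents do not support that: for PPV23 recipients, SAEs after Week 8 appear in the second summary. Nor do they support reading the 58% to 71% of time as a loss of events, since they give no SAE incidence or time pattern. It is also tempting to say that the 1.82% bound in sSAP 3.9.2 would describe only eight weeks, but that section claims no time window.

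**Conclusion.** The point holds as an internal contradiction in current sSAP text with a definite consequence: no specified analysis yields the Day 1 to Month 6 proportion of vaccine-related SAEs by PCV group, although this is one of the three primary safety endpoints. The same applies to any SAE and death.

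The post-PCV summary covers 29% to 42% of follow-up time, which rests only on the protocol's visit windows. How many related SAEs lie outside it cannot be stated, and there may be few if they cluster early.

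The gap for children who miss PPV23 is conditional. It requires a missed dose, continued follow-up and an SAE or death after Week 8, and it assumes a literal reading of the Week 8 limit for a child who has no PPV23 date. The number is unknown and probably small. Some of these children may have stopped for medical reasons, but protocol 7.1 also lists request, unblinding and pregnancy, so they cannot be presumed to be the most informative for safety.

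**What to change.** Reconcile sSAP 3.1, 3.4.2 and 3.6.2 with Table 3 before unblinding:

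1. Specify one count per participant from Day 1 through Month 6 for vaccine-related SAE, any SAE and death. Group by the PCV actually received, take all PCV-vaccinated participants as the denominator whether or not PPV23 was given, and give Clopper-Pearson 95% CIs. Make this the primary analysis of the vaccine-related SAE endpoint.
2. Keep the windows before and after PPV23 as supplementary tables.
3. Write the windows into the SAE and death rows of Table 3.
4. Record the changed window in 3.6.2 in the change log as a substantive change, with its reason.

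The cost is sSAP wording and one extra table from data already collected. The reported V114 SAE percentage may be somewhat higher than in the Week 8 table, because more follow-up is counted.
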